### 10.3 Withdrawal from Study

A subject will be withdrawn from the study for any of the following reasons:

- Lost to follow-up
- Withdrawal of consent
- Death

If a subject discontinues the study before the end of the treatment phase, obtain end-of-treatment and follow-up assessments.

In case a subject is lost to follow-up, every possible effort must be made by the study site personnel to contact the subject and determine the reason for discontinuation/withdrawal. The measures taken to follow up must be documented.

When a subject withdraws before completing the study, the reason for withdrawal is to be documented in the CRF and in the source document. Subjects who withdraw will not be replaced.

## 11 STATISTICAL METHODS

In general, all continuous endpoints will be summarized using descriptive statistics, which will include the number of subjects, mean, standard deviation, median, minimum, and maximum. All categorical endpoints will be summarized using frequencies and

percentages. For time to event variables (eg, overall survival), the Kaplan-Meier method will be used for descriptive summaries. No formal hypothesis testing will be performed.

### **11.1 Subject Information**

The safety population, which includes all subjects who receive at least one administration of siltuximab, will be used in all statistical analyses.

### **11.2 Sample Size Determination**

The sample size for this study is not designed according to statistical calculation. It is expected that up to 75 subjects could be enrolled. The number of subjects enrolled will be determined by the eligible subjects from the C0328T03 and CNTO328MCD2001 studies.

### **11.3 Safety Analyses**

Adverse events, deaths, and safety-related laboratory tests will be summarized as follows:

- Incidence of all AEs
- Incidence of Grade 3 or higher AEs
- Incidence of SAEs
- Incidence of AEs and SAEs reasonably related to siltuximab
- Incidence of clinically important changes in safety-related laboratory parameters
- Incidence of deaths and malignancies
- Incidence of antibodies to siltuximab

### **Adverse Events**

The original terms used in the CRFs by investigators to identify adverse events will be coded using the MedDRA. All reported adverse events with onset on or after the first siltuximab administration through 30 days after the last siltuximab administration within the 6-year data cutoff (ie, treatment-emergent adverse events) will be included in the analysis. The incidence of treatment-emergent AEs will be summarized overall, by MedDRA system-organ class (SOC) and preferred term, by toxicity grade, and by relationship to siltuximab administration. The adverse events of clinical interest, such as infections, hyperlipidemia, neutropenia, thrombocytopenia, GI perforations, infusion-related reactions, liver enzyme abnormalities, and immunogenicity will be summarized in similar fashion.

Special attention will also be given to those subjects who died, or who discontinued treatment due to an adverse event, or who experienced a severe or a SAE (eg, summaries, listings, and narrative preparation may be provided, as appropriate).

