6. SAFETY

Safety analyses will be based on safety population. Safety evaluation will focus on AEs, clinical hematology and chemistry laboratory tests. The overall safety of long-term treatment with siltuximab will be assessed via evaluation of AEs occurred from both parent study and extension study. In the long-term safety extension study, safety monitoring will consist of continuous AE reporting with a focus on infections, hyperlipidemia, neutropenia, thrombocytopenia, GI perforations, infusion-related reactions, liver function, and immunogenicity.

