6.3. Adverse Events of Clinical Interest

6.3.1. Infusion-Related Reactions (IRR)

Number of subjects with any IRR associated with siltuximab administration during the long-term extension study will be summarized by MedDRA system-organ class and preferred term. Note that IRR was not collected in parent study C0328T03.

A listing of subjects with Grade 3 or higher treatment-emergent infusion-related reactions associate with siltuximab administration will be provided.

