6.3.2. Infections and Infestations

A summary of number of subjects with 1 or more toxicity Grade 3 or 4 treatment-emergent infections and infestations by MedDRA preferred term and relationship to siltuximab treatment will be provided.

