6.3.3. Secondary Malignancies

A listing of subjects who reported secondary malignancies during the study will be provided. The listing will include subject ID, diagnosis, study day of diagnosis, recurrence of a prior existing malignancy (yes, no) and stage of disease etc. information whenever a second primary malignancy is observed. In addition, treatment related to secondary malignancy, a total of siltuximab dose received, whether or not subject received subsequent MCD therapy information will also be presented in the listing.

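### SAP 6.3 gives no grouped subject-level summary for five of the Protocol's eight adverse events of clinical interest, and its infection table leaves out Grades 1, 2 and 5

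*Protocol*

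**What the plan says.** Protocol 11.3, under Adverse Events, first sets out how treatment-emergent adverse events (TEAEs) are summarized: overall, by system organ class (SOC) and preferred term, by grade, and by relationship to siltuximab. It then turns to a named set, "The adverse events of clinical interest, such as infections, hyperlipidemia, neutropenia, thrombocytopenia, GI perforations" and others, and closes with "infusion-related reactions, liver enzyme abnormalities, and immunogenicity will be summarized in similar fashion".

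SAP 6 repeats the topics: "safety monitoring will consist of continuous AE reporting with a focus on infections, hyperlipidemia, neutropenia, thrombocytopenia, GI perforations", followed by infusion reactions, liver function and immunogenicity.

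SAP 6.3, the section on adverse events of clinical interest, has three parts:

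- 6.3.1: "Number of subjects with any IRR associated with siltuximab administration during the long-term extension study will be summarized" by SOC and preferred term, with a listing at Grade 3 or higher.
- 6.3.2: "A summary of number of subjects with 1 or more toxicity Grade 3 or 4 treatment-emergent infections and infestations by MedDRA preferred term" and relationship.
- 6.3.3: "A listing of subjects who reported secondary malignancies during the study will be provided". This topic is not in the Protocol's sentence on events of clinical interest.

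Antibodies to siltuximab are covered in SAP 7.2.

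**The concern.** Long-term safety is the primary objective and no hypothesis is tested, so the descriptive adverse event tables are the study's main result. The Protocol singles out a short list of risks for attention, and the SAP section that should carry this out leaves out five of them. For those five, the SAP neither says which reported terms count as the topic nor plans a count of subjects with at least one such event. If a topic is reported under several preferred terms, each row understates it. With no term list fixed in the SAP, any grouping made later would be made with the data in view.

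For infections the dedicated table stops at Grade 4. A subject whose only severe infection was fatal would not be counted in it.

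**Working it through.** No sample size, power or error rate bears on this point. The check takes the Protocol's eight topics one by one and looks for each in the SAP.

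| Protocol 11.3 topic | Own summary in the SAP | Where else it appears |
|---|---|---|
| Infusion-related reactions | 6.3.1, extension only | TEAE tables in 6.1 |
| Infections | 6.3.2, Grade 3 or 4 only | All-grade SOC row in 6.1.2; fatal cases in 6.2.2 |
| Immunogenicity | 7.2 | – |
| Hyperlipidemia | None | Preferred-term rows in 6.1; lipid panel in 6.4 |
| Neutropenia | None | Preferred-term rows in 6.1; neutrophils in 6.4 |
| Thrombocytopenia | None | Preferred-term rows in 6.1; platelets in 6.4 |
| Liver enzyme abnormalities | None | Preferred-term rows in 6.1; AST, ALT, bilirubin and alkaline phosphatase in 6.4 |
| GI perforation | None | Preferred-term rows only (6.1; 6.2.2 if fatal) |

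Count: 1 + 1 + 1 + 5 = 8. Of the five without a summary, 4 have a laboratory counterpart and 1 (GI perforation) has none.

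**Can preferred-term rows replace a grouped count?** SAP 6.1 counts a subject once per SOC or preferred term. For a topic reported under terms with n1, n2, … subjects, the number with any of them lies between max(n1, n2, …) and n1 + n2 + …, and the rows cannot say where. All figures here are assumed:

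- Two terms with 5 and 4 of 75 subjects: between 5/75 = 6.7% and 9/75 = 12.0%.
- Three terms in 8%, 7% and 5% of subjects: between 8% and 8% + 7% + 5% = 20%.

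The lower end needs complete overlap and the upper end needs none. A SOC row would settle the count only if the topic were the SOC. That holds for infections, but the SAP ties none of the five to a SOC.

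**Can the exposure-adjusted rates replace it?** SAP 6.1.1 to 6.1.3 plan them for selected TEAEs without naming which. The time at risk ends at first onset of the event concerned, so a topic's rate needs the first onset across all its terms and cannot be built from term-level rates.

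**Can the laboratory tables replace it?** SAP 6.4 plans shifts from baseline to worst grade for each listed analyte. SAP 2.2 confines these to the extension, while adverse events span parent and extension studies. They carry no relationship assessment, which Protocol 11.3 asks for. Protocol 3.1 expects most subjects to be on siltuximab at enrollment, and SAP 6.4 does not say which baseline applies. If it is the extension baseline, shifts for those subjects start from on-drug values.

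**Infections by grade.** Grades 1 and 2 are in the all-grade SOC row of 6.1.2. Grades 3 and 4 are in 6.1.3 and 6.3.2. Grade 5 is in the all-grade row and, by preferred term, in 6.2.2. Section 6.1.4 gives Grade 3 or higher by SOC, but for related events only. None of the itemised tables gives all infections at Grade 3 or higher. Elsewhere (6.1.4, 6.1.6, 6.1.7, 6.3.1) the SAP uses Grade 3 or higher, as does the Protocol 11.3 list of safety summaries.

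**The case against.** The best defense is that the Protocol's promise is already met. It says only that events such as these are summarized like the others, and SAP 6.1 does that for every TEAE. Neither document promises standardised queries, pooled terms or one table per topic. That stands as far as it goes: the form of the grouping is a recommendation. But the Protocol sentence adds nothing to the one before it unless it means a summary of the named topics, and SAP 6.3 reads it that way for infusion reactions and infections.

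A reader might also infer more than the documents support:

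- *That the five topics have no analysis or incidence.* They do: SAP 6.1 tabulates all TEAEs, and SAP 6.4 gives graded summaries for four of the five.
- *That Grade 1 and 2 infections are lost.* They are not: 6.1.2 has no grade limit, and the count-once rule makes its infections SOC row a proper subject count. Section 6.3.2 is an additional table.
- *That no exposure-adjusted rate is planned for these risks.* The terms are unnamed, so these topics are neither promised a rate nor excluded.
- *That restricting infusion reactions to the extension is an oversight.* SAP 6.3.1 gives the reason: they were not collected in C0328T03.

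Finally, SAP 2.5 refers derived variables to a data presentation specification that is not among the documents. Groupings there cannot be ruled out, though the SAP does not point to it for this purpose.

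**Conclusion.** The point holds as a gap between Protocol 11.3 and SAP 6.3. Five of eight named topics lack a grouped subject-level summary, and the dedicated infection table omits Grades 1, 2 and 5. The information is collected and mostly reported, but indirectly, with GI perforation least covered. It would go too far to say that the safety question is left unanswered: no estimate is invalidated and no data are lost. The change is still worth making, because these tables serve the primary objective.

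The size of any understatement cannot be derived from the documents. The percentages above are assumed illustrations, and they matter only where a topic is reported under more than one preferred term. The conclusion also assumes that no grouping is defined in the unseen specification.

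**What to change.** In SAP 6.3:

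1. For each of the five topics, fix a term list before database lock, either a MedDRA standardised query or a listed set of preferred terms.
2. For each topic, tabulate the number and percentage of subjects with at least one event, at any grade and at Grade 3 or higher, by relationship to siltuximab.
3. Name these groups among the selected TEAEs that receive the exposure-adjusted rate already planned in 6.1.1, using first onset of any term in the group.
4. Change 6.3.2 to all grades, with a row for Grade 3 or higher that includes Grade 5.

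If the data presentation specification already holds such groupings, a reference to it in 6.3 would cover the first step. The cost is agreeing the term lists and programming a few more tables. No new data are needed.

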**Clinical Laboratory Tests**

Hematology and chemistry laboratory values will be summarized at baseline and at each scheduled timepoint by descriptive statistics for each type of laboratory test. The changes from baseline results will also be summarized. In addition, the worst toxicity grade experienced by a subject during the study will be summarized, and shift tables from baseline to worst toxicity during the study will be presented.

**Vital Signs**

Descriptive statistics of temperature, pulse, respiratory rate, and blood pressure (systolic and diastolic) (supine or standing) values and changes from baseline will be summarized at each scheduled time point. The percentage of subjects with values beyond clinically important limits will be summarized.

**ECG**

Abnormal 12-lead ECG findings during treatment will be presented in listings.

**11.4 Efficacy and Patient-reported Outcomes Analyses****11.4.1 Disease Control**

Investigator assessment of disease control for all treated subjects will be analyzed. Specifically, the proportion of previously responding subjects and siltuximab-naïve subjects who maintain disease control will be summarized. The duration of disease control, defined as the time from the first siltuximab administration to disease progression as assessed by the investigator, will also be summarized.

**11.4.2 Laboratory Evaluations**

Efficacy-related laboratory assessments of ESR, CRP, and fibrinogen will be summarized by descriptive statistics at baseline and each scheduled timepoint. The changes from baseline results will also be summarized.

**11.4.3 Overall Survival**

Overall survival is defined as the time between the first study siltuximab administration and death. Subjects who died, regardless of the cause of death, will be considered as an event. Subjects who withdraw consent from the study will be censored at the time of withdrawal. Subjects who are still alive at the cutoff date of the final analysis will be censored at the date of last known alive. All subjects who are lost to follow-up before the 6-year data cutoff will be censored at the date they are last known to be alive.

The Kaplan-Meier method will be used to estimate the distribution of overall survival. Median overall survival with 95% CI will be provided. In addition, the Kaplan-Meier overall survival curve will also be provided.

#### **11.4.4 MCDSS Evaluations**

The patient-reported MCDSS total score at each timepoint and the change from baseline in MCDSS total score will be summarized.

#### **11.5 Glycoform Analysis and In Vivo Protein Degradation**

These analyses will be reported in a separate technical report.

#### **11.6 Pharmacodynamic Biomarker Analyses**

Determination of IL-6 levels prior to first administration of siltuximab is planned to be performed. Exploratory evaluation of IL-6 splice variant analysis may also be performed. Results from IL-6 analysis will be summarized at the timepoints tested and association with clinical response may be explored.

#### **11.7 Interim Analysis**

No later than 2 years after start of enrollment, an interim analysis will be conducted to further evaluate the benefit and safety of long-term treatment with siltuximab in subjects with MCD. In addition, the interim analysis results will be used to support internal decision-making.

### **12 ADVERSE EVENT REPORTING**

Timely, accurate, and complete reporting and analysis of safety information from clinical studies are crucial for the protection of subjects, investigators, and the sponsor, and are mandated by regulatory agencies worldwide. The sponsor has established Standard Operating Procedures (SOPs) in conformity with regulatory requirements worldwide to ensure appropriate reporting of safety information; all clinical studies conducted by the sponsor or its affiliates will be conducted in accordance with those procedures.

#### **12.1 Definitions**

##### **12.1.1 Adverse Event Definitions and Classifications**

###### **Adverse Event**

An adverse event is any untoward medical occurrence in a clinical study subject administered a medicinal (investigational or non-investigational) product. An adverse event does not necessarily have a causal relationship with the treatment. An adverse event can therefore be any unfavorable and unintended sign (including an abnormal finding), symptom, or disease temporally associated with the use of a medicinal (investigational or non-investigational) product, whether or not related to that medicinal (investigational or non-investigational) product. (Definition per International Conference on Harmonisation)

This includes any occurrence that is new in onset or aggravated in severity or frequency from the baseline condition, or abnormal results of diagnostic procedures, including laboratory test abnormalities.

Note: The sponsor collects adverse events starting with the signing of the informed consent form (refer to Section 12.2.1, All Adverse Events for time of last adverse event recording).

### **Serious Adverse Event**

A serious adverse event as defined by ICH is any untoward medical occurrence that at any dose meets any of the following conditions:

- Results in death
- Is life-threatening  
(The subject was at risk of death at the time of the event. It does not refer to an event that hypothetically might have caused death if it were more severe.)
- Requires inpatient hospitalization or prolongation of existing hospitalization
- Results in persistent or significant disability/incapacity, or
- Is a congenital anomaly/birth defect

Note: Medical and scientific judgment should be exercised in deciding whether expedited reporting is also appropriate in situations other than those listed above. For example, important medical events may not be immediately life threatening or result in death or hospitalization but may jeopardize the subject or may require intervention to prevent one of the outcomes listed in the definition above (eg, suspected transmission of an infectious agent by a medicinal product is considered a SAE). Any adverse event is considered a SAE if it is associated with clinical signs or symptoms judged by the investigator to have a significant clinical impact.

### **Unlisted (Unexpected) Adverse Event/Reference Safety Information**

This is defined as an unlisted adverse event, the nature or severity of which is not consistent with the applicable product reference safety information. For an investigational product, the expectedness of an adverse event will be determined by whether or not it is listed in the Investigator's Brochure.

### **Associated With the Use of the Drug**

An adverse event is considered associated with the use of the drug if the attribution is possible, probable, or very likely by the definitions listed in Section 12.1.2.

#### **12.1.2 Attribution Definitions**

##### **Not related**

An adverse event that is not related to the use of the drug.

**Doubtful**

An adverse event for which an alternative explanation is more likely, eg, concomitant drug(s), concomitant disease(s), or the relationship in time suggests that a causal relationship is unlikely.

**Possible**

An adverse event that might be due to the use of the drug. An alternative explanation, eg, concomitant drug(s), concomitant disease(s), is inconclusive. The relationship in time is reasonable; therefore, the causal relationship cannot be excluded.

**Probable**

An adverse event that might be due to the use of the drug. The relationship in time is suggestive (eg, confirmed by dechallenge). An alternative explanation is less likely, eg, concomitant drug(s), concomitant disease(s).

**Very likely**

An adverse event that is listed as a possible adverse reaction and cannot be reasonably explained by an alternative explanation, eg, concomitant drug(s), concomitant disease(s). The relationship in time is very suggestive (eg, it is confirmed by dechallenge and rechallenge).

**12.1.3 Severity Criteria**

Severity of adverse events will be graded according to the NCI-CTCAE Version 4.0, using these descriptors:

- **Grade 1:** Mild AE
- **Grade 2:** Moderate AE
- **Grade 3:** Severe AE
- **Grade 4:** Life-threatening or disabling AE
- **Grade 5:** Death related to the AE

For any event not covered by the NCI-CTCAE, an assessment of severity grade will be made using the following general categorical descriptors:

**Mild:** Awareness of symptoms that are easily tolerated causing minimal discomfort and not interfering with everyday activities.

**Moderate:** Sufficient discomfort is present to cause interference with normal activity.

**Severe:** Extreme distress causing significant impairment of functioning or incapacitation. Prevents normal everyday activities.

The investigator should use clinical judgment in assessing the intensity of events not directly experienced by the subject (eg, laboratory abnormalities).

## **12.2 Procedures**

### **12.2.1 All Adverse Events**

All adverse events, whether serious or non-serious, will be reported from the time a signed and dated informed consent form is obtained until 30 days after last study agent administration. The only exception is for subjects who have withdrawn informed consent for study participation or for subjects who have received additional treatment with therapeutic intent for MCD within 30 days after the last study agent administration. For subjects who have received additional treatment with therapeutic intent for MCD during the AE reporting period, only AEs that are considered to be possibly, probably, or definitely related to study agent must be reported (unless the subject has been withdrawn from the study). Serious adverse events, including those spontaneously reported to the investigator within 30 days after the last dose of study drug, must be reported using the Serious Adverse Event Form. The sponsor will evaluate any safety information that is spontaneously reported by an investigator beyond the time frame specified in the protocol. Key safety events of interest (see the current Investigator's Brochure), including infections, hyperlipidemia, neutropenia, thrombocytopenia, GI perforations, infusion-related reactions, liver enzyme abnormalities, and immunogenicity.

After the 6-year data cutoff, subjects who do not have access to commercially available siltuximab may continue to receive treatment provided by the Sponsor. For these subjects only, SAEs (information on study agent administration and concomitant medications use to treat the SAEs) and pregnancies will have to be reported and collected after the data cutoff at 6 years. These events will be reported to the appropriate health authorities in safety update reports.

All events that meet the definition of a SAE will be reported as SAEs, regardless of whether they are protocol-specific assessments. All adverse events, regardless of seriousness, severity, or presumed relationship to study therapy, must be recorded using medical terminology in the source document and the CRF. Whenever possible, diagnoses should be given when signs and symptoms are due to a common etiology (eg, cough, runny nose, sneezing, sore throat, and head congestion should be reported as “upper respiratory infection”). Investigators must record in the CRF their opinion concerning the relationship of the adverse event to study therapy. All measures required for adverse event management must be recorded in the source document and reported according to sponsor instructions.

The sponsor assumes responsibility for appropriate reporting of adverse events to the regulatory authorities. The sponsor will also report to the investigator all SAEs that are unlisted (unexpected) and associated with the use of the drug. The investigator (or sponsor where required) must report these events to the appropriate Independent Ethics

Committee/Institutional Review Board (IEC/IRB) that approved the protocol unless otherwise required and documented by the IEC/IRB.

Subjects (or their designees, if appropriate) must be provided with a “study card” indicating the name of the investigational study drug, the study number, the investigator’s name, a 24-hour emergency contact number, and, if applicable, excluded concomitant medications.

Disease progression should not be recorded as an adverse event or SAE term; instead, signs and symptoms of clinical sequelae resulting from disease progression/lack of efficacy will be reported if they fulfill the adverse event or SAE definition (see Section 12.1.1 Adverse Event Definitions and Classifications).

